4.2. Background

LY3202328 is a low solubility, highly permeable molecule with high oral exposure in preclinical species. Oral bioavailability at the predicted human 80% maximal effective dose (ED₈₀) efficacious dose (13 mg once daily [QD]) is greater than 30% in preclinical species and is predicted to be 89% in humans. As the dose increases, exposures are expected to increase until reaching a plateau as absorption limitations are expected in humans for doses above 190 mg due to the solubility characteristics of the compound. In vivo, LY3202328 exhibits near linear increases in area under the plasma concentration-time curve (AUC) at doses up to 100 mg/kg with much lower than dose proportional increases in exposure above 100 mg/kg. The maximum plasma concentration (C_{max}) also increases with dose in a less than proportional manner. The time to reach C_{max} (T_{max}) is reached between 1 to 3 hours in most preclinical species.

LY3202328 is eliminated predominantly by cytochrome P450 (CYP) 3A4 microsomal oxidation with <5% of dose excreted as parent by renal elimination. Based on in vitro data, LY3202328 is also a time-dependent inhibitor of CYP3A4 at high concentrations. However, lack of accumulation upon multiple dosing in vivo suggests that LY3202328 does not inhibit its own metabolism. These properties suggest a potential for DDIs with concomitantly administered CYP3A4 substrates (particularly those with a narrow therapeutic margin) or CYP3A4 inhibitors. Half-life in animal preclinical toxicology studies ranged from 3 to 12 hours, yet exposures in rat and dog toxicology studies showed no accumulation of LY3202328 after 28 days of repeat dosing. In humans, LY3202328 is projected to have a half-life of 6 to 8 hours. Human clinical dose projections based on Simcyp modeling of animal PK data predict a dose of 13 mg to achieve an average steady state concentration of 325 ng/mL (equivalent to a 24 hour AUC of 7.8 µg x h/mL) which is associated with 80% efficacy based on preclinical pharmacology studies (after correction for species difference in protein binding and receptor affinity).

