In 28-day repeat dose Good Laboratory Practice (GLP) toxicology studies conducted at doses up to 500 mg/kg in rat and 250 mg/kg in dog (maximum feasible dose levels), no dose-limiting toxicities and no observable adverse effects were observed in either species. In rats administered 500 mg/kg, animals had minimal decreases in body weight gain (4%). Slight hypertrophy observed in liver centrilobular hepatocytes, adrenal zona fasciculata cells, and thyroid follicular cells correlated with minimal organ weight increases. These findings were consistent with

physiological adaptations to stress or minimal metabolic induction commonly observed in rodents. In dogs administered 250 mg/kg, there were infrequent emesis, liquid feces, and minor body weight loss (1%) with reduced food consumption. Rats and dogs administered 500 mg/kg and 250 mg/kg, respectively, had slight decreases in red blood cell mass (red blood cell count, hemoglobin concentration, and hematocrit) with evidence of regeneration based on higher absolute reticulocyte count. These effects observed in rats and dogs were not observed at the end of the 1-month reversibility phase of either study. The effects observed in rats and dogs were monitorable and there were adequate margins to the proposed clinical doses.

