8.1. Treatment Administered

This study involves a comparison of LY3202328 to placebo when administered orally as a single dose in Part A and when administered in multiple doses both with and without a statin (simvastatin or atorvastatin) in Part B. [Table GSEA.2](#) shows the treatment regimens.

In Part A, LY3202328 or placebo will be administered orally in the morning of Day 1 with approximately 240 mL of room temperature water in a sitting position. Subjects will not be allowed to lie supine for 2 hours after dosing, unless clinically indicated or for study procedures.

In Part B, all study drugs will be administered orally in the morning with approximately 240 mL of room temperature water. Simvastatin or atorvastatin will be administered on Day -7.

LY3202328 or placebo will be administered QD on Days 1 to 29 while confined to the CRU (on Days 1 to 3, 7, 14, and 21) or at home. Simvastatin or atorvastatin will be coadministered with LY3202328 or placebo on Day 29 while subjects are confined to the CRU. Investigators should instruct subjects to store the LY3202328 or placebo capsules at home in the original container out of the reach of children at room temperature. Capsules should not be opened, crushed, or dissolved.

Table GSEA.2. Treatments Administered

Treatment Name	LY3202328	Placebo	Simvastatin	Atorvastatin
Dosage Formulation	HPMC capsule	HPMC capsule	Commercial	Commercial
Unit dose strength(s)/ Dosage Level(s)	1, 5, or 50 mg LY Part A: 1, 3, 10, 30, 100, or 300 mg Part B: 5, 20, 100 or 300 mg	Inactive	10 mg	10 mg
Route of Administration	Oral	Oral	Oral	Oral

Abbreviations: LY = LY3202328; HPMC = hydroxypropyl methylcellulose.

The investigator or designee is responsible for:

- explaining the correct use of the investigational product(s) to the subject,
- verifying that instructions are followed properly,
- maintaining accurate records of investigational product dispensing and collection,
- and returning all unused medication to Chorus or its designee at the end of the study.

Note: In some cases, study sites may destroy the material if, during the investigative site selection, the evaluator has verified and documented that the site has appropriate facilities and written procedures to dispose of clinical trial materials.

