6.1.2 Fasting Lipid Profile Analyses in Part B

Fasting lipid profiles will be collected from all subjects in Part B just prior to dosing on the day of dosing, Day 7, Day 14, Day 21, and Day 28, and 7 (Day 35) days after stopping dosing of the randomized treatment. An additional follow-up assessment will be collected 14 (Day42) or 28 (Day 56) days after stopping dosing of the randomized treatment for Cohort 3 (5mg QD) and Cohorts 4 through 6, respectively.

A last on-treatment observation measurement will be derived for each subject using the last post-dose measurement for a lipid parameter taken while the subject is taking study medication during the 28-day treatment period. Change from baseline for each of the lipid parameters will be derived for each of the post-dosing time points (Days 7, 14, 21, 28, 35, and 42 or 56) and the last on-treatment observation using the pre-dose measurement from the first day of dosing as the baseline.

Descriptive statistics for the measurement at baseline and the measurement and change from baseline at each post-baseline time point plus the last observation will be tabulated.

An MMRM analysis will be conducted for each lipid parameter using the change from baseline values from Days 7, 14, 21, 28, 35, and 42. The MMRM model for change from baseline will contain fixed effects for treatment, time, and their interaction, a random effect for subject, and the baseline measurement as a covariate. Since the time points are evenly spaced the covariance structure among the repeated measurements for a subject will be assumed to be common across subjects and modeled using a autoregressive(1) 7x7 matrix. Satterthwaite's approximation will be used to estimate denominator degrees of freedom. Any missing assessments will be assumed to be missing at random, so estimates of treatment effects from the model will be unbiased.

These analyses will be performed using the SAS procedure PROC MIXED. The tabular output for these MMRM analyses will present the least squares means, standard errors and 95% confidence intervals and Type 3 p-values for each main effect marginal. Pairwise contrasts of the least squares means between the LY dose levels and placebo along with the associated 95% confidence interval and Type 3 p-values will also be provided at each time point using LSMESTIMATE statements.

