7.3.2 Clinical Laboratory Analyses in Part B

For Part B, blood samples will be collected on Day -1 then pre-dose on Days 2, 7, 14, 21, and 29 and during follow-up on Days 35 and 42 or 56 for all subjects in Part B.

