7.3.2.2 Clinical Laboratory Shift Tables in Part B

For each treatment group shift tables will be generated from the baseline category to the category at Day 42 or 56 for each laboratory parameter. The shift tables will present the number (percent) of subjects who started in a category (low, normal, high) at baseline and ended in a category at the end of the study. A missing category will be included for both baseline and Day 42 or 56, so that all subjects in the Safety population will be represented in the table. The percentages will be calculated using number of subjects in the Safety population who have measurements at baseline and at Day 42 or 56.

Additional shift tables may be generated if warranted after data review.

Shift tables for the categorical urinalysis parameter will also be produced.

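### Part B laboratory shift tables end at Day 42 or 56, after washout, so no planned table counts subjects with out-of-range values on treatment

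*SAP*

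**What the plan says.** SAP 7.3.2 schedules Part B laboratory samples on Day -1, "then pre-dose on Days 2, 7, 14, 21, and 29 and during follow-up on Days 35 and 42 or 56". Two kinds of table follow for numeric results.

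- SAP 7.3.2.1 gives descriptive statistics for the value and its change from Day -1 at each visit, without reference to the normal range.
- SAP 7.3.2.2 gives the low/normal/high tables: "shift tables will be generated from the baseline category to the category at Day 42 or 56". On the denominator it says: "The percentages will be calculated using number of subjects in the Safety population who have measurements at baseline and at Day 42 or 56". Anything further is discretionary: "Additional shift tables may be generated if warranted after data review".

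On dosing, Protocol 8.1 states: "LY3202328 or placebo will be administered QD on Days 1 to 29". SAP 7.1.1 also lists a Day 29 dose.

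Protocol 11.3.1.2 names clinical laboratory abnormalities in the primary endpoint and commits to summarizing categorical endpoints by subject counts and percentages. For two other safety domains in Part B, vital signs (SAP 7.4.2.3) and QTcF (SAP 7.5.2.2), the SAP does plan counts of subjects with notable values while on treatment.

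**The concern.** A shift table answers the question of how many subjects moved out of range. Here the end of the shift is a visit well after the drug has been stopped. A subject who is out of range at all five on-treatment draws and back in range at follow-up is counted as having had no shift. The table measures recovery, but it is the only categorical summary of numeric laboratory data and so will be read as the summary of abnormalities.

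The time off drug may also differ between columns. If the Day 42 visit belongs to Cohort 3 and Day 56 to Cohorts 4 to 6, the 5 mg column is read at a shorter interval than the other three doses, and the pooled placebo column mixes the two.

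The nonclinical data show why this could matter. Protocol 4.2 reports slight falls in red cell mass in rats and dogs, and then: "These effects observed in rats and dogs were not observed at the end of the 1-month reversibility phase of either study". A human effect that reversed in the same way would not appear in a Day 56 table. Protocol 10.4.4 itself applies the reference range on treatment, defining anemia during dosing as hemoglobin or hematocrit below normal. No planned table counts the subjects who meet that definition.

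**Working it through.** **1. Time from last dose to the tabulated visit.** SAP 6.1.2 gives its own intervals: "An additional follow-up assessment will be collected 14 (Day42) or 28 (Day 56) days after stopping dosing of the randomized treatment". These reproduce only if dosing stops on Day 28: 42 − 28 = 14 and 56 − 28 = 28. With the last dose on Day 29:

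- Day 42: 42 − 29 = 13 days = 312 h
- Day 56: 56 − 29 = 27 days = 648 h

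**2. In half-lives.** Protocol 4.2: "In humans, LY3202328 is projected to have a half-life of 6 to 8 hours".

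- Day 42: 312/8 = 39 to 312/6 = 52
- Day 56: 648/8 = 81 to 648/6 = 108

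**3. Which draws can set the category.** Post-baseline draws are Days 2, 7, 14, 21, 29, 35 and 42/56, seven in all. Assume 40 subjects and full attendance.

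| Draws | Per subject | Total | Able to set the category |
|---|---|---|---|
| On treatment (Days 2, 7, 14, 21, 29) | 5 | 40 × 5 = 200 (LY3202328: 32 × 5 = 160) | 0 |
| Day 35 | 1 | 40 | 0 |
| Day 42 or 56 | 1 | 40 | 40 |

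The Day 29 draw is pre-dose, so Day 35 is the first scheduled draw after the combined LY3202328 and statin dose, and it is unused too. A worst-value table through Day 35 would search 40 × 6 = 240 draws.

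**4. Time off drug by column.** SAP 6.1.2 assigns Day 42 to Cohort 3 and Day 56 to Cohorts 4 to 6, but says so only for lipid profiles. If the same holds for laboratory tests:

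| Group | Read at 13 days | Read at 27 days |
|---|---|---|
| LY3202328 | 8 (5 mg) | 3 × 8 = 24 (20, 100, 300 mg) |
| Pooled placebo | 2 | 3 × 2 = 6 |

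**5. Can the by-visit statistics supply the count?** SAP 2.8 prints n, mean, SD, median, minimum and maximum. Take an invented row for one dose group at one visit: n 8, mean 34.5, SD 16.55, median 32.5, minimum 16, maximum 60, with an assumed upper limit of 40. Listing every set of eight integers that fits (sum 8 × 34.5 = 276) gives 21 sets:

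- 9 sets have 2 values above 40
- 9 sets have 3
- 3 sets have 4

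For example, {16, 21, 21, 32, 33, 35, 58, 60} has 2 and {16, 20, 21, 23, 42, 43, 51, 60} has 4. In both, the squared deviations sum to 1918, and √(1918/7) = 16.55. The same printed row therefore fits 25% to 50% of subjects out of range. Linkage across visits is also lost: one high value at each of the five on-treatment visits could be anything from 1 to 5 different subjects.

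**6. Early leavers.** Protocol 9.1 and 9.2 give them end-of-study procedures. The SAP does not say whether those results fill the Day 42/56 cell. If they do not, these subjects fall in the missing category and outside the percentages.

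**The case against.** The strongest reply is that on-treatment abnormalities are not lost.

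- **Adverse event tables.** Protocol Appendix 1 allows an abnormal laboratory finding to be an adverse event, and SAP 7.2 then counts subjects by preferred term and severity. This is true, but only for findings recorded as events, and Protocol 11.3.1.2 lists laboratory abnormalities separately from adverse events.
- **By-visit statistics.** A slight fall in red cell mass is a continuous change. It would appear in SAP 7.3.2.1 and might never cross a range limit, even in a worst-value table. This stands: such an effect would not go unreported. The minimum and maximum also show whether anyone in a group was out of range at a visit. What is missing is how many subjects, and which ones across visits. The animal findings also arose at exposures 13 to 15 times those predicted at 300 mg (Protocol 6.5), so they may not occur here.
- **Discretion to add tables.** SAP 7.3.2.2 and Protocol 11.3.1.2 both allow further analysis after data review, and SAP 1.1 lets supportive analyses be added without amendment. The route is open but names no visit. Because SAP 2.1 lets all sponsor personnel be unblinded to a cohort once its dosing is complete, the choice could be made with treatment known. The companion table formats were not available, but SAP 1.1 describes them as formats for outputs in the SAP, which describes no such table.
- **Support for the size.** Plasma half-lives do not measure laboratory recovery, and the split by cohort is carried over from the lipid section. Protocol 6.1.2 schedules Day 56 for every Part B cohort; on that schedule all columns would be read at 27 days. Both caveats stand. Neither brings the tabulated visit into the dosing period.
- **Consequence.** Dose escalation and subject monitoring rely on separate review, and the study is descriptive and unpowered. This stands and limits the point to end-of-study reporting.

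**Conclusion.** The concern holds and should be fixed. As written, the one categorical summary of numeric laboratory results in Part B describes subjects 13 or 27 days after the last dose, and none of the 200 planned on-treatment draws can affect a completer's category. A named component of the primary endpoint is therefore counted only after washout.

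The intervals rest on the Day 29 last dose, which both documents state. The assignment of Day 42 to 5 mg and Day 56 to the higher doses rests on the lipid section of the SAP. The half-life figures use a projection from before any human data and show only that the drug should be gone by then. The documents give no rate of laboratory abnormalities, so the number of subjects that would be missed cannot be stated.

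**What to change.** In SAP 7.3.2.2, pre-specify for Part B a shift table from baseline to the worst post-baseline value:

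- lowest and highest values in separate tables, unscheduled results included;
- draws after the first dose through Day 35, with the on-treatment draws (Days 2 to 29) identifiable;
- denominator: Safety Population subjects with a baseline and at least one post-dose value.

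Keep the Day 42/56 table, label it as a recovery table, and state which cohorts have which visit and how early-termination results are mapped to it. By-visit shift tables would also give on-treatment counts, but would not link subjects across visits.

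The cost is SAP wording and additional tables from data already being collected.

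Two side items could be settled in the same edit. SAP 7.4.2 keeps unscheduled vital signs out of summary tables while SAP 7.4.2.3 includes them; the two should be reconciled. The Part A shift, which ends at 96 h, could use the worst of the 24, 48 and 96 h values in each period.

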11.3.1.2. Statistical Evaluation of Safety

The primary endpoint of this study is the number and severity of treatment-emergent adverse events (TEAEs), clinical laboratory abnormalities, changes in vital sign measurements, and other safety endpoints after administration of LY3202328 or placebo. Summary statistics will be provided by dose group and for all study subjects combined wherever appropriate. For

continuous variables, summary statistics will include number of subjects, mean, median, SD, minimum, and maximum. Categorical endpoints will be summarized using number of subjects, frequency, and percentages. Additional analysis will be performed if warranted upon review of the data.

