7.3.1.2 Clinical Laboratory Shift Tables in Part A

Each laboratory parameter will be classified as low, normal or high relative to the central laboratory's normal range. For each treatment group shift tables will be generated from the pre-dose category to the category 96 hours post-dose for each laboratory parameter. The shift tables will present the number (percent) of subjects who started in a category (low, normal, high) at baseline and ended in a category at the end of the study. A missing category will be included for both pre-dose and 96-hours post-dose, so that all subjects in the Safety population will be represented in the table. The percentages will be calculated using number of subjects in the Safety population who have measurements at pre-dose and 96-hours post-dose.

Shift tables comparing pre-dose to the other time points in the study may be generated if warranted after data review.

Similar shift tables for the categorical urinalysis parameter will also be produced using all categories reported for a parameter during the study.

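### The SAP's only committed categorical summary of hematology and chemistry is a shift to the last visit, which for Part B completers is 13 or 27 days off drug, and no table counts ULN-multiple crossings or pairs ALT/AST with bilirubin

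*SAP*

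**What the plan says.** - **Categories.** SAP 7.3.1.2: "Each laboratory parameter will be classified as low, normal or high" against the central laboratory's range. No multiple of the ULN appears.
- **Time point.** Part A shifts run from pre-dose to 96 hours. Part B shifts run "from the baseline category to the category at Day 42 or 56 for each laboratory parameter" (SAP 7.3.2.2). SAP 6.1.2 assigns the two late visits "for Cohort 3 (5mg QD) and Cohorts 4 through 6, respectively", that is, Day 42 for Cohort 3 and Day 56 for the others. Both shift sections allow further shift tables after data review, without naming a time point, trigger or limit.
- **Sampling.** SAP 7.3.2: "blood samples will be collected on Day -1 then pre-dose on Days 2, 7, 14, 21, and 29", then Day 35 and Day 42 or 56.
- **Dosing.** Protocol 8.1: "LY3202328 or placebo will be administered QD on Days 1 to 29". SAP 7.1.1 also lists a Day 29 dose.
- **Endpoint.** Protocol 11.3.1.2 defines the primary endpoint as the "number and severity of treatment-emergent adverse events (TEAEs), clinical laboratory abnormalities" and other safety measures.
- **Liver limits.** Protocol 10.4.4 starts monitoring at ALT or AST ≥3x ULN, or ALP, GGT or total bilirubin ≥2x ULN. Protocol 9.1 has discontinuation considered at, among others, ALT or AST >8x, >5x for more than 2 weeks, >3x with bilirubin >2x, and ALP >3x.
- **Other on-treatment summaries.** SAP 7.3.2.1 gives descriptive statistics by visit. SAP 7.4.2.3 and 7.5.2.2 count Part B subjects beyond numeric limits for vital signs and QTcF, using every on-treatment value including unscheduled ones, and give flagged listings for both parts.
- **Urinalysis.** "Similar shift tables for the categorical urinalysis parameter will also be produced" (SAP 7.3.1.2), with a matching line for Part B. Categorical urinalysis is outside this point.

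**The concern.** A shift to a late follow-up visit describes recovery, not occurrence. An ALT rise on Day 14 or Day 29 that has settled by the last visit is tabulated as normal-to-normal. If the subject entered above the ULN, which inclusion criterion 7 allows up to 1.5x for ALT, AST, GGT and ALP, a rise that falls back to the entry level is tabulated as high-to-high. In neither case does the table show how high the value went.

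What is at stake is the final report's account, by dose group, of one component of the primary endpoint. A reader deciding on the next study will want to know how many subjects per dose crossed the protocol's own liver limits, and whether any subject had ALT or AST and bilirubin raised together. The SAP prespecifies neither.

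Reversal over such an interval is plausible for laboratory effects of this compound. Protocol 4.2 reports that the slight red-cell-mass decreases seen in rats and dogs at the top doses were absent after a 1-month recovery phase. The Day 56 visit comes 27 days after the last dose.

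**Working it through.** **1. Gap from last dose to the categorised visit.** SAP 6.1.2 gives 14 and 28 days after stopping dosing. That is reproduced by counting from Day 28: 42 − 28 = 14 and 56 − 28 = 28. With the Day 29 dose counted:
- Cohort 3: 42 − 29 = 13 days
- Cohorts 4 to 6: 56 − 29 = 27 days

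Protocol 4.2 states that "LY3202328 is projected to have a half-life of 6 to 8 hours". So 13 days (312 h) is 312/8 = 39 to 312/6 = 52 half-lives, and 27 days (648 h) is 648/8 = 81 to 648/6 = 108. This shows only that the visit is off drug; it says nothing about how fast an enzyme recovers.

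**2. Scheduled visits categorised (completers).**

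| | Post-baseline visits | Categorised |
|---|---|---|
| Part B, on treatment | Days 2, 7, 14, 21, 29 (5) | 0 of 5 |
| Part B, all | the above plus Day 35 and Day 42 or 56 (7) | 1 of 7 |
| Part A, each period | 24, 48, 96 h (3) | 1 of 3 |

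These counts need no assumption beyond completion of the schedule.

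**3. Illustration of a rise that the shift would miss.** Let b be the baseline and P a Day 29 peak, both in ULN units, and let the excess halve every h days. The value at the last visit is b + (P − b)·2^(−gap/h), which is ≤1x ULN when h ≤ gap / log2((P − b)/(1 − b)). Example: b = 0.5, P = 3, gap = 27 gives 27/log2(5) = 27/2.32 = 11.6 days.

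| b | P | Day 56: h at most | Day 42: h at most |
|---|---|---|---|
| 0.5 | 3 | 11.6 d | 5.6 d |
| 0.5 | 5 | 8.5 d | 4.1 d |
| 0.5 | 8 | 6.9 d | 3.3 d |
| 0.75 | 3 | 8.5 d | 4.1 d |
| 0.75 | 5 | 6.6 d | 3.2 d |
| 0.75 | 8 | 5.6 d | 2.7 d |

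Here b, P and h are assumptions, and the documents give no values for them. A peak before Day 29 leaves longer to resolve. The documents give no frequency of such rises, and none is assumed.

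**4. What the by-visit statistics can recover.** SAP 2.8 gives n, mean, SD, median, minimum and maximum. Together these can bound the count at a visit. Assumed example, 8 subjects, ULN units: minimum 0.4, median 0.6, maximum 3.2, mean 0.93. The sum is 8 × 0.93 = 7.44. Two subjects at ≥3x would need at least 3.2 + 3.0 + 6 × 0.4 = 8.6, so exactly one crossed. A median below 3x alone caps the count at 4 of 8.

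They do not add up across visits. If exactly one subject is ≥3x at each of the 5 on-treatment visits, the number of different subjects lies between 1 (1/8 = 12.5%) and 5 (5/8 = 62.5%). Nor do they pair tests: maxima of ALT 4x and bilirubin 2.5x at one visit fit one paired case or none.

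**The case against.** The other side has several fair points.

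- **Early terminators.** A reader might infer that no on-treatment liver value in Part B can ever be categorised. The documents do not support that. Protocol 9.1 and 9.2 give early discontinuers the end-of-study procedures, and the Part B schedule footnote allows these before early termination. A subject withdrawn for abnormal liver tests could have final labs close to dosing. The SAP does not say how such samples map to Day 42 or 56. The 0-of-5 count therefore applies to completers.
- **By-visit statistics.** A reader might also infer that these leave the count anywhere from 1 to 8 of 8. That uses the maximum alone; the mean, median and minimum narrow the per-visit count considerably. The across-visit count and the pairing remain unavailable.
- **AE reporting.** Investigators must document review of every laboratory report, abnormalities can be recorded as AEs, protocol 11.3.1.1 names a grading scale for AE severity, and SAP 7.2.6 tabulates maximal severity. With 8 active subjects per dose, a marked ALT rise would be hard to overlook. This stands, but the count then depends on what was recorded as an AE.
- **Room to add.** Protocol 11.3.1.2 provides for categorical summaries in general and for further analyses, and SAP 1.1 lets supportive analyses be added without amendment. These are permissions; none fixes a limit, a visit rule or a pairing.
- **Nature of the limits.** Sections 9.1 and 10.4.4 are individual management triggers, not analysis endpoints. True, but they are the protocol's own statement of which values matter.
- **Part A.** For vital-sign and QTcF limits the SAP plans only a listing in Part A, so by its own standard no Part A table is missing.

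**Conclusion.** The point holds for what the SAP commits to. Among Part B completers, the sole committed categorical summary of hematology and chemistry covers 0 of 5 scheduled on-treatment visits and falls 13 or 27 days after the last dose. No planned table in either part counts ULN-multiple crossings or shows ALT/AST and bilirubin together in one subject. The partial cover can bound a per-visit count but does not give a prespecified across-visit count or a pairing.

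The recovery half-times are illustrative and rest on assumed baselines and peaks; they do not show how often a rise would be missed. A reader might also infer a threat to subject safety or to escalation. The documents do not support this: escalation under protocol 8.3.1 rests on safety review, and individual cases are handled under 9.1 and 10.4.4. The consequence is confined to the final report, so this is an inexpensive improvement that should be made. The companion table formats were not available, but SAP 1.1 describes them as formats for the tables in the SAP.

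**What to change.** Keep the existing shift tables. Add to SAP 7.3.2.2 one Part B table by treatment group, counting subjects by worst post-baseline value, whether scheduled, unscheduled or from early termination:

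- ALT or AST ≥3x, >5x and >8x ULN
- ALP ≥2x, >2.5x and >3x ULN
- GGT ≥2x ULN
- total bilirubin ≥2x ULN
- ALT or AST >3x ULN with total bilirubin >2x ULN in the same subject

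For Part A, add only a flagged by-subject listing, following SAP 7.4.2.3 and 7.5.2.2.

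The cost is SAP wording, one table and one listing, from chemistry already collected. The downside is a little extra programming and a sparse table: 9 rows by 5 groups is 45 cells, mostly small or zero with 8 subjects per group. An explicit zero by dose is still useful in a first-in-human report. The table covers liver tests, where the protocol sets ULN-multiple limits; it does not change the hematology summaries.
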